- Intent-to-treat (ITT) population: will consist of all patients who receive at least one dose of study drug.
- Modified ITT (mITT) population: will consist of all patients who receive at least one dose of study drug and who are assigned to a DRC-adjudicated disease category. The mITT population and sub-populations based on DRC-adjudicated disease categories will be used for the analysis of efficacy data.
- Trough PK analysis set (Trough PK set): will include all patients who received at least one dose of study drug and have at least one measured trough F901318 plasma concentration.
- Intensive PK analysis set (Intensive PK set): will consist of a subset of the SAF population who have evaluable [REDACTED] PK data. Further details on sub-categories (dose level and concomitant medication dependent) will be provided in the modelling analysis plan.

General Statistical Considerations:

Data collected in the main study phase up to Day 84/Day 90 and the subsequent 4-week follow-up visit will be included in the data analyses and presented in the clinical study report (CSR). Data collected during ET will not be included in the data analyses or in the CSR, and will be presented in the report addendum.

Analyses will be made using the overall study population and within the DRC-adjudicated baseline disease categories, and will be descriptive in nature. Data will be presented using appropriate summary statistics. Categorical data will be described using absolute and relative frequencies (n and %). Continuous data will be presented using descriptive statistics (n, mean, standard deviation, minimum, median, and maximum). All variables will be listed in individual patient listings, sorted by DRC-adjudicated baseline disease category and patient number.

Given the various patient sub-groups included in this study data may be summarised in the following groupings:

- a) Efficacy for all patients.
- b) Efficacy by baseline DRC-adjudicated infection category (the 5 categories of Inclusion Criterion 6).
- c) Efficacy by disease location (CNS, bone, lung/sinus, skin/subcutaneous, other, disseminated).
- d) Efficacy by underlying condition (haematological malignancy, allogeneic haematopoietic stem cell transplant, solid organ transplant, diabetes, active malignant disease, neutropenia at diagnosis, glucocorticoid use, T-cell immunosuppressant use, renal dysfunction).

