- a. Tissue and cells submitted for histopathologic or cytopathologic studies should be stained by Grocott-Gomori methenamine silver stain or by periodic acid Schiff stain, to facilitate inspection of fungal structures. Whenever possible, wet mounts of specimens from foci related to invasive fungal disease should be stained with a fluorescent dye (e.g. calcofluor or blankophor).
- b. Recovery of *Aspergillus* species from blood cultures invariably represents contamination

Probable Invasive Fungal Disease - Lower Respiratory Tract Disease Invasive Aspergillosis (LRTD IA)

At least one high-risk host factor (definitions see below)

PLUS, at least one clinical feature (definitions see below)

PLUS, at least one mycological criterion (definitions, see below)

Host factors and clinical features are not required for patients with Proven IFD. However, if such host factors and clinical features are present at baseline, they will be recorded in the eCRF.

Definitions of Diagnostic Criteria:

Host Factors:

- Recently resolved (< 4 weeks) or ongoing neutropenia (neutropenia defined as absolute neutrophil count < 0.5×10^9 cells/L [< 500 cells/mm³] for ≥ 10 days), temporally related to the onset of fungal disease.
- Receipt of an allogeneic haematopoietic stem cell transplant (HSCT) or bone marrow transplant (BMT).
- Prolonged use of corticosteroids (excluding among patients with allergic bronchopulmonary aspergillosis) at a mean minimum dose of 0.3 mg/kg/day of prednisone equivalent for > 3 weeks.
- Treatment with other recognized T-cell immunosuppressants, such as cyclosporine, tacrolimus, monoclonal antibodies or nucleoside analogues during the past 90 days.
- Inherited severe immunodeficiency (such as chronic granulomatous disease or severe combined immunodeficiency).

Clinical Features:

Lower Respiratory Tract Fungal Disease

The medical history must be established to exclude alternative aetiologies and to distinguish between an acute or subacute presentation rather than a chronic pulmonary infection. Onset of clinical symptoms and/or physical findings within approximately 2 weeks prior to the first administration of study drug defines an acute or subacute pulmonary infection.

The presence of **at least one** of the following “**specific**” **imaging signs on computed tomography (CT), high resolution computed tomography (HRCT) or magnetic resonance imaging (MRI)**:

- i. Dense well-circumscribed lesion(s) (nodules) with or without halo sign

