7.4. EXAMINATION OF SUBGROUPS

The following subgroups will be presented for DRC-adjudicated overall response, Investigator-assessed overall response, and all-cause mortality. It should be noted that the study was not designed to detect treatment differences with high statistical power within subgroups, therefore this is a descriptive analysis only.

- 1) DRC-Adjudicated Baseline Disease Category and subcategory (patients may be included in more than one aspergillus subcategory)
 - Lomentospora (Scedosporium) prolificans (LoPro)
 - Scedosporium spp.
 - Aspergillus - All

Document: \\ieedc-vnasc01\BIOSdata\F2G\F901318\ [Redacted]
Author: [Redacted] Version Number: 3.0
Version Date: 06Apr2023
Template No.: CS_TP_BS016 Revision 6 Reference: CS_WI_BS005
Effective Date: 02Dec2019

F2G Ltd.
PROTOCOL F901318/0032

- Aspergillus - proven
 - Aspergillus - probable (IA-LRTD)
 - Aspergillus-R*
 - Aspergillus-S *
 - Aspergillus-unknown *
 - Coccidioides
 - Other F901318-susceptible fungi [this would include Fusarium, Phaeoacremon, Scopulariopsis, Histoplasmosis, Madurella, Sporothrix etc.]
- *To determine -azole resistance subcategory, consider the Central and Local Lab Microbiology Data for susceptibility result of 4 -azole drugs (itraconazole, voriconazole, posaconazole, isavuconazole) for the isolate;
 - If aspergillus is resistant to all 4 -azole then consider it as resistant
 - If at least one result is resistant then consider it as resistant
 - If all 4 are susceptible then susceptible
 - If no resistant and at least one susceptible then susceptible
 - If Intermediate and results awaiting then Unknown.

If the patient has a subcategory of “Unknown” using central lab data, or if central lab data was not available, the same criteria will be used to determine -azole resistance subcategory using local microbiology data. The following breakpoints were used to derive susceptibility result for aspergillus tested in the local lab, using MIC reported by the local lab:

- isavuconazole: resistant if MIC >1 ug/mL, susceptible if MIC <=1 ug/mL
- itraconazole: resistant if MIC >1 ug/mL, susceptible if MIC <=1 ug/mL
- posaconazole: resistant if MIC > 0.5 ug/mL , susceptible if MIC <=0.5 ug/mL
- voriconazole: resistant if MIC > 1 ug/mL, susceptible if MIC <=1 ug/mL
- If local MIC test is not available, a positive TR34/L98H test result would also indicate

Document: \\ieedc-vnasc01\BIOSdata\F2G\F901318 [Redacted]
Author: [Redacted] Version Number: 3.0
Version Date: 06Apr2023

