Template No.: CS_TP_BS016 Revision 6 Reference: CS_WI_BS005
Effective Date: 02Dec2019

the isolate would be considered as resistant.

2) Prior antifungal therapy response

- Active (uncontrolled)
- Active (stable)
- Improved
- No therapy/Too brief

If the investigator has entered more than one response for prior antifungal therapy per patient, the worst outcome will be used (i.e. worst=refractory/failing, then stable/persistent, unable to judge, partial, complete)

3) Immunosuppression status

Each subject will be assigned one of 3 categories for immunosuppression status, based upon their underlying disease as completed by the Investigator at time of subject enrolment. Categories will be assigned as follows:

- Highly immunosuppressed will include subjects who have haematological malignancies or have received an haematopoietic stem cell transplantation.
- Moderately immunosuppressed will include subjects who either have immunological disorders (such as AIDS, chronic granulomatous disease and cystic fibrosis) or non-haematological malignancies or who have undergone solid organ transplant
- Low/no immunosuppression will include patients with any other underlying diseases and patients who are immunocompetent.

The immunosuppression category will be assigned as above by manual medical review of underlying disease terms prior to database lock, with appropriate documentation.

A second variant of immune status subgroup using two levels will to also be derived from the above:

- Low/No immunosuppression
- Moderate + High immunosuppression

4) Duration of prior antifungal therapy

Due to potential inconsistency of the investigator-entered categories in eCRF variable, duration of prior antifungal

Document: \\ieedc-vnasc01\BIOSdata\F2G\F901318\ [Redacted]
Author: [Redacted] Version Number: 3.0
Version Date: 06Apr2023
Template No.: CS_TP_BS016 Revision 6 Reference: CS_WI_BS005
Effective Date: 02Dec2019

F2G Ltd.
PROTOCOL F901318/0032

therapy (for systemic antifungal therapy received ≤ 14 days before first dose of study drug) will be calculated using start/stop date of antifungal therapy;

For any systemic antifungal therapy received ≤ 14 days before first dose, calculate total duration of exposure for the patient (i.e. stop date – start date + 1 for each antifungal therapy, and sum up total cumulative duration for the patient adding together exposure if more than one relevant antifungal or if antifungals overlap).

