^a A Baseline visit will be programmatically added to outputs (where applicable) based on the derived baseline flag. ^b Derived End of Treatment visits will be programmatically added to outputs where applicable. ^c In chronological order in between scheduled visits, as applicable. ^d Extended Treatment visit will not be included in outputs but will form part of ADaM datasets.	

LISTINGS

All listings will be ordered by the following (unless otherwise indicated in the template):

- Baseline DRC-adjudicated disease category,
- Patient number,
- Date (where applicable).
- Prior Antifungal Therapyat Time of Enrollment to Olorofim

“Nature of response to prior antifungal therapy at time of enrollment to olorofim trial” in eCRF page “Pre-Study Course for Fungal Infection Under Study”.

CRF Page: Nature of response to prior antifungal therapy at time of enrollment to Olorofim trial?	(To be presented as) Subgroup “ Prior antifungal therapy response ”, categories:
---	---

Document: \\weedc-vnasc01\BIOSdata\F2G\F901318\ [Redacted]
 Author: [Redacted] Version Number: 3.0
 Version Date: 06Apr2023
 Template No.: CS_TP_BS016 Revision 6 Reference: CS_WI_BS005
 Effective Date: 02Dec2019

F2G Ltd.
 PROTOCOL F901318/0032

Refractory / Failing	→	“Active (Uncontrolled)”
Stable / Persistent	→	“Active (Stable)”
Patients with no response entered (missing) or where response is “Unable to judge” (since detail of unable to judge showed all patients had no therapy or too brief)	→	“No therapy/too brief”
Partial	→	“Improved”
Complete	→	“Improved”
Multiple	→	“Multiple”
Note: If we expect multiple responses per patient, use the worst outcome (i.e. worst=refractory/failing, then stable/persistent, unable to judge, partial, complete)		

- Immuno suppression status
- Programming note; summary of primary disease type shown below. Medical review and final subgroup categories confirmed in spreadsheet
 “Immunosuppression_F2G_ [redacted] [redacted]”

UDPTCoded	Coded
AIDS	ModIS
CF	ModIS
CGD	ModIS
GenMedical	LowIS
HemeMalig	HighIS
HSCT	HighIS
ImmuneDefect	ModIS
LungTx	ModIS
None	LowIS
NonHemeMalig	ModIS
OtherSOT	ModIS

Document: \\weedc-vnasc01\BIOSdata\F2G\F901318 [redacted]
 Author: [redacted] Version Number: 3.0
 Version Date: 06Apr2023
 Template No.: CS_TP_BS016 Revision 6 Reference: CS_WI_BS005
 Effective Date: 02Dec2019

F2G Ltd.
 PROTOCOL F901318/0032

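### Immunosuppression status is taken from underlying-disease terms alone, so some patients on prolonged corticosteroids or T-cell immunosuppressants are displayed as Low/no in descriptive subgroups

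*SAP*

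**What the plan says.** SAP 7.4 item 3 sets the basis of the variable: "Each subject will be assigned one of 3 categories for immunosuppression status, based upon their underlying disease as completed by the Investigator". Haematological malignancy and stem cell transplant are High. Immunological disorders, other malignancy and solid organ transplant are Moderate. For the remainder, "Low/no immunosuppression will include patients with any other underlying diseases and patients who are immunocompetent". The category is "assigned as above by manual medical review of underlying disease terms prior to database lock". A two-level version (Low/No against Moderate plus High) is built from the same coding.

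The coding map in SAP Appendix 1 (Listings), introduced by "Programming note; summary of primary disease type shown below", has 11 codes. GenMedical and None map to low; the other nine map to moderate or high. No code refers to drug exposure.

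On use, SAP 7.4 says: "The following subgroups will be presented for DRC-adjudicated overall response, Investigator-assessed overall response, and all-cause mortality". SAP 17, 17.1.2 and 17.2 also summarise PK by immune status and give no other definition of it.

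Protocol Appendix 2 requires for Probable LRTD IA: "At least one high-risk host factor (definitions see below"). One such factor is prolonged corticosteroids (a mean of at least 0.3 mg/kg/day prednisone equivalent for more than 3 weeks). Another is "Treatment with other recognized T-cell immunosuppressants, such as cyclosporine, tacrolimus, monoclonal antibodies or nucleoside analogues during the past 90 days". Neither is tied to a diagnosis. The protocol synopsis, under General Statistical Considerations item d, lists among possible efficacy groupings: "neutropenia at diagnosis, glucocorticoid use, T-cell immunosuppressant use, renal dysfunction".

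**The concern.** The two documents can label the same patient in opposite ways. A patient with a non-malignant, non-transplant disease who takes long-term corticosteroids can meet the host requirement for Probable LRTD IA on that ground alone, yet appear in the outcome tables as having low or no immunosuppression.

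Protocol 2.3 treats host immunity as a major prognostic divide: it describes invasive scedosporiosis as lethal in immunocompromised patients and less deadly in healthy hosts. In a single-arm study, readers will use the immune-status table to judge how far response and survival reflect the host rather than the drug. If drug-immunosuppressed patients sit in the Low/no row, that row will tend to look worse than its label implies, and the contrast with the other rows will look smaller.

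**Working it through.** **Step 1: apply the rule.** The documents state no figure for this point, so the check is to trace patients through the SAP rule and the Appendix 1 map.

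| Patient | Appendix 2 drug host factor met? | Category under SAP 7.4 item 3 |
|---|---|---|
| Probable LRTD IA, other medical disease, prolonged corticosteroids | Yes, and sufficient alone for the host requirement | Low/no |
| Proven IFD, other medical disease, T-cell immunosuppressant in past 90 days | Yes, though not needed for entry | Low/no |
| Lung transplant on tacrolimus | Yes | Moderate (LungTx) |
| Haematological malignancy on corticosteroids | Yes | High (HemeMalig) |
| Autoimmune disease on corticosteroids | Yes | Depends on whether the medical review counts it as an immunological disorder |

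The first two rows are the gap. Rows three and four are already classed Moderate or High. Row five is uncertain.

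**Step 2: look for a correction elsewhere.** The medical review works on disease terms and applies the stated rule, so it has no basis for moving a patient because of a drug. The probable-IA subgroup pools all host factors. Neutropenia has its own subgroup (item 6), but corticosteroids and T-cell agents do not. Host factors are tabulated at baseline (SAP 10) and concomitant medications by ATC level 4 (SAP 12), but neither output is crossed with outcome. None of these changes the Low/no label.

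**Step 3: size.** Let f be the share of the Low/no group that is drug-immunosuppressed, p_L the rate in truly low/no patients, and p_H the rate in Moderate plus High. The documents give none of the three; all are assumed. If the misplaced patients behave like Moderate plus High:

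- displayed Low/no rate = (1 − f)·p_L + f·p_H
- displayed contrast = (1 − f)·(p_L − p_H)

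Success, assuming p_L = 50% and p_H = 25% (true contrast 25 points):

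- f = 10%: 0.9 × 50 + 0.1 × 25 = 47.5%; contrast 22.5 points
- f = 20%: 0.8 × 50 + 0.2 × 25 = 45%; contrast 20 points
- f = 40%: 0.6 × 50 + 0.4 × 25 = 40%; contrast 15 points

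Mortality, assuming 20% and 50% (true gap 30 points):

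- f = 10%: 0.9 × 20 + 0.1 × 50 = 23%; gap 27 points
- f = 20%: 0.8 × 20 + 0.2 × 50 = 26%; gap 24 points
- f = 40%: 0.6 × 20 + 0.4 × 50 = 32%; gap 18 points

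If the misplaced patients responded halfway between the groups (37.5%), then at f = 20% the displayed rate would be 0.8 × 50 + 0.2 × 37.5 = 47.5%, half the drop.

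**The case against.** The strongest reply is that little depends on this variable. SAP 7.4 calls the subgroups descriptive, SAP 7.3 applies no multiplicity procedure, and no test or decision uses immune status. That stands, and it limits the point to how the tables are read.

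A reader might infer that the SAP breaches the protocol by omitting glucocorticoid and T-cell immunosuppressant use. The documents do not support that: the synopsis says data may be summarised by those groupings and leaves subgroup detail to the SAP. The visible text of SAP 3.3 does not mention the omission, but an optional grouping left out is not a contradiction.

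A reader might also infer that everyone on these drugs is mislabelled. They are not: many will have a transplant, a malignancy or an immune disorder. The Moderate class is also open-ended on immunological disorders, so review may capture some autoimmune disease.

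It is fair, too, that Appendix 2 host factors support a diagnosis and do not grade immunosuppression, and that Low/no is openly a residual class. But the row will be read by its name, and the protocol itself calls these exposures high-risk.

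Finally, a careless remedy could misclassify in the other direction. Protocol 5.9 and 6.2.6 collect host-factor exposure from the time of initial diagnosis, which may be well before entry. This objection is sound and shapes the fix.

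**Conclusion.** The point holds in a limited form. The written rule places patients with another or no listed underlying disease in Low/no even when they meet the Appendix 2 corticosteroid or T-cell immunosuppressant criterion, and no other planned output corrects the label. It affects the immune-status rows for DRC-adjudicated response, investigator-assessed response and all-cause mortality, and the PK summaries by immune status. It does not touch the primary response rate or its confidence interval.

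The size cannot be determined from the documents. The dilution is proportional to the misplaced share of Low/no, on the assumption that those patients fare like the Moderate and High groups. The shares and rates used above are illustrations; the 40% share in particular has no documentary support and should not be read as an estimate.

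**What to change.** Amend SAP 7.4 item 3 and the Appendix 1 map so that a patient who meets the Appendix 2 corticosteroid or T-cell immunosuppressant criterion, with exposure ongoing at or within 90 days before first dose, is classed at least Moderately immunosuppressed whatever the disease term. The time limit keeps out exposure that ended long before entry. Leave neutropenia to item 6.

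Alternatively, keep the disease-based scale, relabel it as underlying-disease risk, and add glucocorticoid use and T-cell immunosuppressant use as two separate subgroups for the same outcomes. Record whichever choice is made in SAP 3.3.

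The cost is some extra derivation and, under the first option, a smaller Low/no group with wider intervals. No new data are needed: protocol 6.2.3 collects steroid use and duration, protocol 6.2.6 collects T-cell immunosuppressants within 90 days before screening and corticosteroid dosing that supports the host factor, and SAP 10 already summarises host factors.

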5.9.2 Allowed Medications

See Section 5.9 for a general discussion of concomitant medications.

5.9.2.1 *Candida Prophylaxis and Concomitant Antifungal Therapy*

F901318 is not active against yeast infections and the use of fluconazole for prophylaxis or treatment of concomitant candidiasis is permitted at any time due to fluconazole's lack of activity against mould fungi. Patients who are receiving treatment with isavuconazole or posaconazole should be switched to receive treatment with fluconazole. Should a patient start or stop receiving fluconazole treatment whilst on study, an extra visit for Unscheduled Trough PK sampling will occur 3 to 5 days after starting or stopping such concomitant medication. This Unscheduled Trough PK sample will be sent for rapid trough PK analysis of F901318, to assess the impact of any dose adjustment made.

In order to meaningfully analyse the efficacy of F901318, it is important to avoid concomitant use of other systemic antifungal agents with known or potential activity against the primary fungal infection. That said, the constraints on choice of additional agents may be complex and thus use of any other systemic concomitant antifungal or combination treatment (such as addition of terbinafine for confirmed *Lomentospora prolificans* infections or an echinocandin to manage infection due to *Candida*) is permitted but is discouraged.

For all other infections, antifungal combinations should be based on the Investigator's clinical judgement with efforts made to minimize use where possible. Use of concomitant antifungal therapy must be discussed and agreed with the MM.

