Patients will be assigned to subgroup category based on total cumulative duration;

- No prior antifungal therapy 2 weeks prior to study
- 1-7 days
- 8-14 days
- 15-28 days
- 29-90 days
- 91-180 days
- >180 days

Duration category of prior antifungal therapy entered into the eCRF by the investigator is available, but categories overlap and may not be accurate. Subgroup levels will be derived using start and stop dates entered into the eCRF for prior therapy.

Duration of prior antifungal therapy – two level

Using the same calculation as the duration of prior antifungal therapy above, patients will be assigned to a two-level subgroup category based on total cumulative duration;

- 0-28 days
- >28 days

Patients with no prior therapy will be included in the first level of the categories as “0 days”.

5) Malignancy type

Malignancy status will be derived for each patient based on primary underlying disease type entered into the eCRF,

Document: \\ieedc-vnasc01\BIOSdata\F2G\F901318 [redacted]
Author: [redacted] Version Number: 3.0
Version Date: 06Apr2023
Template No.: CS_TP_BS016 Revision 6 Reference: CS_WI_BS005
Effective Date: 02Dec2019

and medical review of malignancy type.;

- Haem-malignancy
 - Non haem-malignancy
 - No malignancy
 - Not applicable
- 6) Neutropenia status
- Neutropenia at screening
 - No neutropenia.

Patients who have neutropenia onset date within 28 days prior to first dosing (instead of any onset date prior to treatment start date) date and still ongoing at screening/baseline (i.e. not resolved prior to first dose date) will be categorised as “Neutropenia at screening”, otherwise patients will be categorised as “No neutropenia”.

7) Reason for Limited Treatment Options

Reason for Limited Treatment Options will be analysed as a 4-level variable for the subgroup analysis, by grouping the criteria for meeting limited alternative treatment options described in the Study Synopsis as follows:

- Known or predicted resistance to all licensed agents (including Known or predicted Resistance, Need oral – azole and -azole resistance is known, Need oral – azole and -azole resistance predicted by PCR, Need oral – azole and -azole resistance is predicted epidemiologically)
- Failure of available therapy (including Failure of available therapy, Inability to produce therapeutic drug levels, MM Approval.
- Intolerance to available therapy (including Intolerance to available therapy)

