12. MEDICATIONS

Concomitant and prior Antifungal Medications will be coded using the most recent version of World Health Organisation Drug Dictionary (WHO-DD) and descriptive statistics by ATC level 4 for all concomitant medications

Document: \\weedc-vnasc01\BIOSdata\F2G\F901318\ [Redacted]
Author: [Redacted] Version Number: 3.0
Version Date: 06Apr2023
Template No.: CS_TP_BS016 Revision 6 Reference: CS_WI_BS005
Effective Date: 02Dec2019

and antifungal concomitant medications based on the ITT analysis set will be presented.

See [appendix 2](#) for handling of partial dates for medications, in the case where it is not possible to define a medication as prior, concomitant or post the medication will be classified by the worst case; i.e. concomitant. A medication may be classed as both 'prior' and 'concomitant'.

- 'Prior' medications are medications which were started prior to the first dose of study medication.
- 'Concomitant' medications are medications which were:

started prior to, on or after the first dose of study medication but prior to last dose of study medication,

AND ended on or after the date of first dose of study medication or were ongoing at the end of the study.

- 'Post' medications are medications started after the last dose of study medication (to be listed only).
- Therapeutic drug monitoring data on medications resulting in dose adjustments will be listed.
- Concomitant antifungal usage (Yes/No)
 - number of days of concomitant antifungal usage on study
- Summary will be presented by systemic antifungal medication and non-antifungal medications. Systemic antifungals will be confirmed and provided by medical review process.
- Plot for duration of antifungal medications will also be presented.

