APPENDIX 2. PARTIAL DATE CONVENTIONS

Imputed dates will NOT be presented in the listings.

ALGORITHM FOR TREATMENT-EMERGENCE OF ADVERSE EVENTS:

START DATE	STOP DATE	ACTION
Known	Known/Partial/ Missing	If start date < study med start date, then not TEAE If start date >= study med start date, then TEAE
Partial, but known components show that it cannot be on or after study med start date	Known/Partial/ Missing	Not TEAE
Partial, could be on or after study med start date OR Missing	Known	If stop date < study med start date, then not TEAE If stop date >= study med start date, then TEAE
	Partial	Impute stop date as latest possible date (i.e. last day of month if day unknown or 31st December if day and month are unknown), then: If stop date < study med start date, then not TEAE If stop date >= study med start date, then TEAE
	Missing	Assumed TEAE

Document: \\ieedc-vnasc01\BIOSdata\F2G\F901318\

Author:

Version Number:

3.0

Version Date:

06Apr2023

Template No.: CS_TP_BS016 Revision 6

Reference: CS_WI_BS005

Effective Date: 02Dec2019

F2G Ltd.
PROTOCOL F901318/0032

ALGORITHM FOR PRIOR, CONCOMITANT AND ANTIFUNGAL MEDICATIONS, AND NON-MEDICATION PROCEDURES:

START DATE	STOP DATE	ACTION
Known	Known	
If stop date < study med start date, assign as prior
 
If study med start date <= stop date <= end of treatment and start date < study med start date assign as both prior and concomitant
 
If study med start date <= start date <= end of treatment assign as concomitant
 
If start date > end of treatment, assign as post study

	Partial	
Impute stop date as latest possible date (i.e. last day of month if day unknown or 31st December if day and month are unknown), then:
 
If stop date < study med start date, assign as prior
 
If study med start date <= stop date <= end of treatment and start date < study med start date assign as both prior and concomitant
 
If study med start date <= start date <= end of treatment assign as concomitant
 
If start date > end of treatment, assign as post treatment

	Missing	
If start date < study med start date assign as both prior and concomitant
 
If study med start date <= start date <= end of treatment, assign as concomitant
 
If start date > end of treatment, assign as post treatment

Document: \\weedc-vnasc01\BIOSdata\F2G\F901318\ [Redacted]

Author: [Redacted] Version Number: 3.0

Version Date: 06Apr2023

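### SAP 7.4 item 4 counts antifungal days after first dose as prior therapy, so a baseline subgroup depends partly on survival and time on drug during the study

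*SAP*

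**What the plan says.** SAP 7.4 presents seven sets of subgroups for DRC-adjudicated overall response, Investigator-assessed overall response and all-cause mortality, and calls the analysis descriptive.

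Item 4 takes any systemic antifungal received within 14 days before first dose and says to "calculate total duration of exposure for the patient (i.e. stop date – start date + 1 for each antifungal therapy", then to "sum up total cumulative duration for the patient adding together exposure if more than one relevant antifungal or if antifungals overlap". Patients go into seven levels, and also into a two-level split at 28 days. On the source of dates it says: "Subgroup levels will be derived using start and stop dates entered into the eCRF for prior therapy".

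Other sections show that a course may cross first dose:
- SAP 12 defines the term by start date alone: prior "medications are medications which were started prior to the first dose of study medication". It adds: "A medication may be classed as both" prior and concomitant.
- SAP Appendix 2 codes that case. For a drug stopped during treatment, the rule reads "and start date < study med start date assign as both prior and concomitant".
- Protocol 5.9.2.1 says "the use of fluconazole for prophylaxis or treatment of concomitant candidiasis is permitted at any time". Other systemic antifungals are allowed but discouraged.
- SAP 12 has a separate output for the "number of days of concomitant antifungal usage on study".

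SAP 12.1 uses the same duration formula. It replaces a missing stop date, for prior or concomitant drugs, with the end of main-phase treatment. Item 4 does not cite that rule.

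**The concern.** A subgroup used to describe outcome should be fixed before treatment starts. Here a patient with few pre-dose days can enter a long-duration level only by being alive and still taking the drug some weeks into the study. Mortality is then reported by that level. A reader would take the rows as showing how outcome varies with earlier antifungal treatment, when part of the difference could come from how patients were sorted into rows.

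Two neighbouring items raise a smaller issue, of labels only. Item 6 calls a patient 'No neutropenia' if the episode is unresolved at first dose but began more than 28 days before it. Item 7 places criterion 7f(i)-(iii) patients, who responded to an IV-only option and have known, predicted or suspected azole resistance, under resistance to all licensed agents. It places criterion 7g patients, who by definition meet none of a) to f), under failure of available therapy.

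**Working it through.** The documents give no figure for this point, so there is nothing to reproduce. The check applies the SAP formula to example dates.

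**Inputs.** Duration = stop - start + 1 (SAP 7.4 item 4). Day 1 is first dose and there is no Day 0 (SAP 6.1). Levels are those of item 4.

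**Formula.** A course from Day -k to Day T has k days before first dose and T days from first dose on. The SAP score is k + T; the pre-dose duration is k.

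| Course | SAP score | Level (two-level) | Pre-dose days | Level (two-level) |
|---|---|---|---|---|
| Day -20 to 14 | 20 + 14 = 34 | 29-90 (>28) | 20 | 15-28 (0-28) |
| Day -5 to 42 | 5 + 42 = 47 | 29-90 (>28) | 5 | 1-7 (0-28) |
| Day -10 to 84 | 10 + 84 = 94 | 91-180 (>28) | 10 | 8-14 (0-28) |

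All three have known stop dates, so no imputation is involved. If the third course is fluconazole, the row applies only if fluconazole is counted as a relevant systemic antifungal.

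**When the two-level split flips.** k + T > 28 first holds at T = 29 - k: Day 24 for k = 5, Day 19 for k = 10, Day 15 for k = 14, Day 9 for k = 20.

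**Missing stop dates.** There are two readings. If the SAP 12.1 rule feeds item 4, T becomes the last day of main-phase treatment. With k = 5, treatment ending on Day 10, 84 or 90 gives 15, 89 or 95 days. If only entered dates are used, item 4 has no rule for a missing stop date.

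**Could it matter for mortality?** The share of courses that run on is not in the documents, so this is illustration only. Assume pre-dose courses uniform on 1 to 56 days, no true effect of duration, constant hazard, and 10%, 25% or 50% of courses continuing to death or Day 84. In a simulation of 300,000 patients per scenario, Day 42 mortality in '0-28' against '>28' was:
- at 30% overall mortality: 30.8% v 29.4%, 32.5% v 28.4%, 36.8% v 27.6%;
- at 15% overall mortality: 15.4% v 14.8%, 16.3% v 14.2%, 19.0% v 13.6%.

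Between about 4% and 24% of patients changed level. With the count cut at the day before first dose, the two levels agreed to within about 0.3 points.

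**Items 6 and 7.** Unresolved neutropenia with onset on Day -28 is labelled 'Neutropenia at screening'; with onset on Day -29 it is 'No neutropenia'. In item 7, three of the four reason codes in the first level require a prior response to an IV-only option. That counts codes, not patients.

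**The case against.** The best defence is that the intent is plainly pre-study. Item 4 replaces an investigator-entered category for prior therapy, draws on dates recorded for prior therapy, has a lowest level defined by the two weeks before the study, and sits beside a separate output for on-study antifungal days. All of that is fair, and it makes the defect one of wording. But naming the source of dates sets no cut, and under SAP 12 a prior drug may end during the study. A programmer following the text would count the whole course.

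A second objection stands in part. Item 4 speaks of relevant antifungals, SAP 12 leaves confirmation of systemic antifungals to medical review, and Protocol 5.9.2.1 notes that fluconazole lacks activity against moulds. A reader might infer that all continued fluconazole is counted; the documents leave that open. Without it the affected group is smaller, since other systemic antifungals are discouraged on study and patients on isavuconazole or posaconazole should be switched to fluconazole.

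Third, the effect may be small beside sampling error. Assuming 200 patients split evenly and 30% mortality, the 95% half-width for a difference is 1.96 x sqrt(2 x 0.30 x 0.70 / 100) = 12.7 points, against a 1.4-point gap in the 10% scenario above. That is a fair measure of scale, but no reason to keep an avoidable distortion.

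On items 6 and 7 the defence is largely right. The 28-day onset limit is stated as a deliberate choice, Exclusion Criterion 7 narrows the group by excluding neutropenia not expected to resolve, item 7 lists its components, and single reasons are tabulated at baseline (SAP 10). Only the row labels remain at fault.

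**Conclusion.** The point holds for item 4: as written, the rule puts days after first dose into a variable presented as prior therapy. For one course the excess is T days, the last on-study day of that drug. This rests on the printed text of SAP 6.1, 7.4 and 12 and needs no assumption about imputation.

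A reader might go further and infer that long prior treatment will look protective by some known amount. The documents do not support that. They do not say how many courses cross first dose, and a drug kept going may equally mark a sicker patient, so the overall size and direction for response and mortality are not established. Nor can one infer that the SAP 12.1 imputation certainly applies; that is likely from the shared formula but is not stated. The main efficacy result is not at risk: the subgroups are descriptive, and the mITT Day 42 response rate does not use this variable.

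The matter deserves correction before the tables are run, but is not critical. The issues in items 6 and 7 are labels only; neither the 28-day window nor the pooling is hidden or wrong in itself.

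**What to change.** **Item 4.** State that days are counted only up to the day before first dose, truncating any course that stops on or after first dose or is ongoing. State that the SAP 12.1 imputation to main-phase treatment end does not apply to this subgroup. Flag courses whose end date is unknown rather than ongoing: cutting them at the day before first dose gives only the longest possible pre-dose duration and overstates any course that ended earlier. Say whether medical review counts fluconazole as relevant. Adding together overlapping drugs is an explicit SAP choice and can stay, provided the table says that the total is in drug-days.

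**Item 6.** Keep the 28-day window and put the onset limit in both level names.

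**Item 7.** Rename or footnote the two pooled levels so that 7f(i)-(iii) patients are not shown simply as resistant to all licensed agents, nor 7g patients simply as failures of available therapy.

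**Cost.** SAP wording and minor reprogramming. Antifungal dates, neutropenia episodes and reason codes are already collected. Relabelling makes no cell smaller, and the cut only moves patients between existing levels of item 4.
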